#### 7.3. Inclusion – Surgical patients

- Adult  $\geq$  18 years
- Patients admitted to RSFT for planned major surgery

#### 7.4. Exclusion – Surgical patients

- Prisoners
- Anticipated prohibitively difficult venous cannulation
- Presenting with inflammatory diseases and disorders including but not limited to arthritis, peripheral artery disease, vasculitis, sepsis, diabetes with end organ damage, cardiovascular disease and CKD
- Currently prescribed immunomodulatory medication or immunocompromised
- Received chemotherapy within 2 weeks of predicted sampling
- Receiving vasopressor support prior to surgery
- History of recent major trauma within the last 2 months (e.g., surgery or injury requiring hospitalisation)

#### 7.5. Inclusion – Critically ill patients

- Adult ≥ 18 years
- Emergency admission to ICU at RSFT
- Meets the sepsis 3.0 definition

#### 7.6. Exclusion – Critically ill patients

- Prisoners
- Anticipated prohibitively difficult venous cannulation
- Presenting with inflammatory diseases and disorders including but not limited to arthritis, peripheral artery disease, vasculitis, diabetes with end organ damage, cardiovascular disease and CKD.
- Currently prescribed immunomodulatory medication or immunocompromised
- Received chemotherapy within 2 weeks of predicted sampling.
- History of recent major trauma within the last 2 months (e.g., surgery or injury requiring hospitalisation)

### 7.7. Justification for using healthy volunteers

We are using healthy volunteers in this study to compare baseline mRNA expression to sepsis patients and surgery patients. This is because we want to isolate the effects of sepsis and surgery from other factors, such as the presence of other medical conditions or medications. Healthy volunteers are less likely to have confounding factors that could interfere with the results of our study.

## 7.8. Incentivisation of healthy volunteers

Staff at RSFT and staff and students at UOS were interviewed on how to best incentivise healthy volunteers' participation and compensation for their time. A consensus agreement was reached suggesting that financial compensation would most appropriate. A median answer of £20 was suggested.

Healthy volunteers will be remunerated £20 for their participation in this study.

### Trial procedures

## 7.9. Recruitment and screening

All patients will be identified from the electronic records systems at RSFT, by theatre lists or from referral by clinical staff. The study will use summary posters placed in staff areas to promote recruitment.

Screening of patients will be done by checking clinical notes and from verbal confirmation from the participant. Patients who decline to participate or fail to meet eligibility will have the reason documented on the screening log. The PI or delegate can confirm eligibility.

Healthy volunteers will be made up of members of staff and volunteers at RSFT and students at UoS. They will be identified by email advertisement from each individual organisation. All correspondence between volunteers and study team will be through the PI to maintain confidentiality. The wider study team will only be able to access anonymised date.

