## 3. Protocol Summary

Title	Characterization of endothelial cells in multiple inflammatory pathologies			
Short title	JEDI-2			
Sponsor	Royal Surrey NHS Foundation Trust			
Design	Prospective observational study of three cohorts: i) healthy volunteers, ii) surgical patients, iii) critically ill patients.			
Primary objectives	To identify the changes in mRNA expression in endothelial cells from surgical patients and sepsis patients			
Secondary objectives	Stratification of patients based on mRNA expression from endothelial cells.			
	Characterisation of microparticles, histones and cell free DNA.			
Target accrual	Part 1: 25 healthy volunteers, 20 patients with sepsis and 20 elective abdominal surgery			
	Part 2: 20 patients with sepsis and 20 elective abdominal surgery			
Inclusion criteria (both parts)	
 
≥18 Years old
 
At RSFT for either and emergency admission to ICU, an elective surgery or as a healthy volunteer.
 
			
Exclusion criteria (both parts)	
 
Prisoners
 
Anticipated prohibitively difficult venous cannulation
 
Presenting with inflammatory diseases and disorders including but not limited to arthritis, peripheral artery disease, vasculitis, diabetes with end organ damage, cardiovascular disease and CKD.
 
Currently prescribed immunomodulatory medication or immunocompromised
 
Received chemotherapy within 2 weeks of predicted sampling.
 
History of recent trauma
 
			
Number of sites	1			
Duration of recruitment	12-18 months			
Duration of patient follow-up	Up to 28 days			
Definition of end of trial	End of follow-up of last patient			

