### 7.1. Inclusion – Healthy volunteer

- Adult ≥ 18 years
- Able and willing to give consent

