#### 7.2. Exclusion – healthy volunteer

- Not currently a patient within the hospital
- Absence of inflammatory diseases and disorders including but not limited to arthritis, peripheral artery disease, vasculitis, diabetes, cardiovascular disease and CKD.
- Not on immunomodulatory medications, such as corticosteroids

- History of recent major trauma within the last 2 months (e.g., surgery or injury requiring hospitalisation)
- •

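### The protocol makes no provision to balance the Part 1 healthy controls to the patients on age

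*Protocol*

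**What the plan says.** Section 6 describes Part 1 as a one-timepoint comparison of acutely inflamed patients with a healthy control. The study overview in 6.1 says that Part 2 then follows the genes of interest found in Part 1.

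The controls are described in 7.9: "Healthy volunteers will be made up of members of staff and volunteers at RSFT and students at UoS". They are found by email advertisement. The inclusion criteria in 7.1 are age 18 or over and "Able and willing to give consent". There is no age band, upper limit or matching step. Section 10.1 plans 25 volunteers, 20 for analysis and 5 for method validation, against 20 patients per cohort.

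Section 7.7 gives the purpose of the controls: "we want to isolate the effects of sepsis and surgery from other factors, such as the presence of other medical conditions or medications".

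On diabetes, the inclusion row of the Protocol Summary covers all three groups ("At RSFT for either and emergency admission to ICU, an elective surgery or as a healthy volunteer"), and its single exclusion list reads "peripheral artery disease, vasculitis, diabetes with end organ damage, cardiovascular disease and CKD". Section 7.2, for volunteers, reads "vasculitis, diabetes, cardiovascular disease and CKD", with no qualifier. The patient lists keep the qualifier: "vasculitis, sepsis, diabetes with end organ damage, cardiovascular disease and CKD" in 7.4 and "vasculitis, diabetes with end organ damage, cardiovascular disease and CKD" in 7.6.

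**The concern.** Part 1 is a between-person contrast. A gene that varies with age, but not with sepsis or surgery, will look differentially expressed if the groups differ in age. False discovery rate control does not protect against this, because it limits chance findings and not systematic group differences. The sample size in 10.1 assumes that disease is the only systematic difference between the groups.

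The pool of staff, hospital volunteers and students is a convenience sample. Nothing in the protocol makes its ages follow those of patients having planned major surgery or admitted to ICU with sepsis. Who is enrolled cannot be repaired at the analysis stage: if no older controls are recruited, a model term has little overlap to work with. What is at stake is a partly biased gene list and Part 2 effort spent on false leads.

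**Working it through.** **Inputs from Protocol 10.1.** 20,000 genes, 90% unchanged, FDR 0.05, power 0.8, fold change 2 (1 log2), mean count 10, dispersion 0.1, 20 per group recruited. Every age shift, share of affected genes and age gap below is an assumption, because the protocol gives none.

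**The plan's own figure.** The stated n is 16 per group. ssizeRNA was not available, so negative binomial counts with t-tests on log counts and Benjamini-Hochberg at 0.05 were used instead. Simulated power is 0.78 at n = 15, 0.83 at n = 16 and 0.93 at n = 20, so 16 reproduces.

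**Per-gene false calls at 20 v 20.**
- Per-gene level: 0.8 × 0.1 × 0.05 / (0.9 × 0.95) = 0.00468.
- SD on the log2 scale: √(1/10 + 0.1) / ln 2 = 0.645.
- SE of the difference: 0.645 × √(2/20) = 0.204. Critical t on 38 df is 3.005.
- Noncentral t probability that a gene with no disease effect is called:

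| Shift (log2) | 0 | 0.2 | 0.3 | 0.4 | 0.6 |
|---|---|---|---|---|---|
| Probability | 0.005 | 0.029 | 0.076 | 0.166 | 0.483 |

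**False share of the whole list.** Count simulation, 2,000 of 20,000 genes truly changed by 1 log2 up or down, 8 runs per cell. With no gene shifted the false share is 0.042.

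| Unchanged genes affected | 0.2 | 0.3 | 0.4 | 0.6 |
|---|---|---|---|---|
| 1% | 0.046 | 0.048 | 0.055 | 0.081 |
| 5% | 0.054 | 0.067 | 0.105 | 0.212 |
| 10% | 0.062 | 0.097 | 0.160 | 0.345 |

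Hand check of the last cell: 1,800 × 0.483 = 869 shifted genes are called, plus 16,200 × 0.00468 = 76 others, against 2,000 × 0.911 = 1,822 true ones. The share is 945 / 2,767 = 0.34, in agreement.

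**The same in years.** Assume a within-group age SD of 10 years and 5% to 10% of genes changing 1.1- to 1.2-fold per decade (2 runs per setting, so approximate). The unadjusted false share is 0.05 to 0.08 at a 10-year gap, 0.06 to 0.19 at 20 years and 0.10 to 0.46 at 30 years. The top value exceeds the table because the shift is then larger: 3 × log2(1.2) = 0.79.

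**What adjustment for age costs.** For a gap of d within-group SDs between equal groups, the variance of the group effect is inflated by 1 + d²/4, that is 1.25, 1.56 and 2.0 at d = 1, 1.5 and 2. Holding the per-gene level at 0.00468 gives power 0.906, 0.810 and 0.673, against 0.964 with no gap. These values are too favourable, because the Benjamini-Hochberg cutoff tightens as power falls. Count simulations give average power for a 2-fold change of about 0.9 with no gap, 0.8 at 1 SD, 0.6 to 0.7 at 1.5 SD and 0.4 to 0.6 at 2 SD. Ranges are quoted because the runs are few.

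**Diabetes.** If 7.2 governs, the mean shift in an affected gene is prevalence × effect. Assuming 10% of patients and 0.5 log2 gives 0.05 and a false-call probability of 0.006. Assuming 30% and 1 log2 gives 0.3 and 0.076.

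**The case against.** **No ages are given.** A reader might infer that the controls will be younger than the patients, or that the groups are unbalanced. The documents do not support that: the pool includes staff and hospital volunteers, so older controls are possible. Only the absence of any step to secure balance can be asserted.

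**Adjustment can sit in the analysis plan.** This is correct, and a missing covariate in the outline in 10.4 is not a fault. Demographics are collected in every cohort, and adjustment alone works for a modest gap. It does not replace recruitment when the gap is large, as the power figures show.

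**Part 2 limits the harm.** Section 6 presents Part 2 as validation, and its surgical schedule has a pre-surgery biopsy, so purely age-driven genes can drop out within patients. This largely stands. The sepsis schedule starts on admission and has no pre-illness sample, and Part 2 looks only at genes already chosen.

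**The diabetes conflict is editorial.** The summary's exclusion list resembles the patient lists and may never have been meant for volunteers, and barring diabetes is part of what makes a control healthy. This mostly stands. A reader might take the conflict as a major source of bias, but the figures above do not support that. The summary's inclusion row nevertheless names healthy volunteers, so the two texts do disagree.

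**Banding has costs.** It slows volunteer recruitment, and one control set cannot match two cohorts exactly. Both points stand and are counted below.

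**Conclusion.** The point holds as an avoidable design weakness. The protocol fixes a convenience source for the controls and has no step to bring their ages into line with the patients', while 7.7 relies on them to isolate disease effects and Part 2 relies on the resulting list.

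The size is unknown. Under the assumed shifts the false share goes from about 4% to between 5% and 35%, and the upper part of that range needs several percent of genes to shift by about 0.4 log2 or more. Nothing in the protocol shows whether that condition holds. It would go too far to conclude that the Part 1 list will be wrong or that the study's final conclusions are invalid. The supportable harm is false leads carried into Part 2. The change is worth making because it is cheap and cannot be made after recruitment.

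The diabetes wording is secondary. The summary and 7.2 conflict for volunteers, and 7.2 states most of its items as absences under an exclusion heading, so read literally it excludes healthy people.

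**What to change.** **In 7.9:**
- Fill the 20 analysed control places by broad age band, and by sex where feasible, to the combined distribution of the accruing patient cohorts.
- Exempt the 5 method-validation volunteers, so that early laboratory work is not delayed.
- Name a wider source in case the email pool cannot fill the older bands.
- Use age and sex as model terms for residual imbalance.

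**Wording:**
- Reconcile the volunteers' diabetes criterion between the Protocol Summary and 7.2, and reword 7.2 so that its items are exclusions.
- If 7.2 governs, patients may have uncomplicated diabetes and controls may not. In that case limit the statement in 7.7 accordingly, or add a sensitivity analysis without diabetic patients. If 10% to 30% of patients were diabetic, 18 to 14 would remain against 20 controls, with power of about 0.95 to 0.91 (same fixed-level approximation, so somewhat optimistic).

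**Cost.** Text changes only, with no added participants or procedures. Volunteer recruitment becomes slower and tied to patient accrual, which matters with one recruiter and a 12-month estimate for Part 1 (10.3). A wider source adds work, and one control set will only approximate both patient cohorts. If banding proves impractical, adjustment alone is acceptable for a gap of up to about 1 SD.

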## 7.10. Consent

The PI retains overall responsibility for the conduct of research at their site, this includes the taking of informed consent of participants at their site. They must ensure that any person delegated responsibility to participate in the informed consent process is duly authorised, trained and competent to participate according to the ethically approved protocol, principles of GCP and Declaration of Helsinki. If delegation of consent is acceptable then details should be provided.

Informed consent or agreement must be obtained prior to the participant undergoing procedures that are specifically for the purposes of the trial and are out-with standard routine care at the participating site. Personal consultees must be contacted first before approaching a professional consultee.

The right of a participant to refuse participation without giving reasons must be respected.

The participants are free to withdraw at any time from the trial without giving reasons and without prejudicing their further treatment and will be provided with a contact point where they may obtain further information about the trial. Data and samples collected up to the

point of withdrawal will be used after withdrawal unless the participant has explicitly said so. The intention to utilise their data is outlined in the consent literature. Where a participant is required to re-consent or new information is required to be provided to a participant it is the responsibility of the PI to ensure this is done in a timely manner.

The PI takes responsibility for ensuring that all vulnerable participants are protected and participate voluntarily in an environment free from coercion or undue influence.

Where the participant population is likely to include a significant proportion of participants who cannot read or write, require translators, or have cognitive impairment, appropriate alternative methods for supporting the informed consent process should be employed. This may include allowing a witness to sign on a participant's behalf (in the case of problems with reading or writing), or allowing someone to date the form on behalf of the participant, or providing Participant Information Sheets in a format easily understood by the participant population (in the case of minors or cognitive impairment).

#### Cohorts:

Healthy volunteers will be consented after the have shown an expression of interest in participating. They can be approached at any time to sign consent after they have registered their interest.

Surgical patients will be consented prior to their surgery. They will be approached by a member of the clinical team to see if they would consider learning more about a potential research opportunity. If they are amenable, a member of the study team will introduce the study and present them with a PIS/ICF to review. This can be done prior to admission using telephone consent or in person on the day of surgery. There will be no deferred consent used.

Sepsis patients will be recruited on admission to ICU. Should the patient have capacity, they will be approached by a member of the clinical team to see if they would consider learning more about a potential research opportunity. If they are amenable, a member of the study team will introduce the study to them and present the PIS. While the patient may have full capacity to make a decision, the anticipated stressful nature of an intensive care admission may leave them in a state where they do not want to read or sign a document. In this case a witnessed verbal agreement to participate will suffice until the patient is ready to sign the consent form. In patients who lack capacity, we will use a deferred consent model. A personal or professional consultee will be consulted. Once the patient has improved, the study team will then seek to be granted consent, retrospectively. If they do not regain capacity, we will still analyse their samples.

Consent procedures can be completed by the PI or delegate. See figure 3 for visualisation.

Figure 3

## 7.11. Baseline data and previous medical history

Information will be obtained from the medical notes following provision of consent by the participant. At time of enrolment we will collect demographic data, past medical history and current medical problems and current medications. Medical history and demographics in healthy volunteers will be collected as an oral history. The study will not look at medical records for this cohort. Data for patient cohorts will be collected from patient notes and from the summary care record from NHS SPINE.

## 7.12. Follow up

Follow up of patients will consist of obtaining their clinical status (Recovered/discharged from hospital/still in hospital/dead) from the patient's clinical notes. This information is to capture any significant clinical events happening after discharge from ICU. No formal contact will be made with the patient, unless there are any outstanding AEs that require resolving. Follow up will take place at 28 days (±2 days) post enrolment.

### 7.13. Withdrawal criteria

It is within the remit of the treating physician to withdraw their patient from the study, if they believe that it is causing them significant harm or inappropriate to perform the procedure. The trial team will also withdraw patients from the study if the patient has suffered an serious adverse event (SAE) as a consequence of the trial procedures. In both cases it must be explicitly documented in the eCRF the reason/s for withdrawal. Participants who are prematurely withdrawn may be replaced at the decision of the study team.

It is the responsibility of the trial site to ensure that samples are appropriately labelled in accordance with the trial procedures to comply with the 1998 Data Protection Act. Biological

samples collected from participants as part of this trial will be transported, stored, accessed and processed in accordance with national legislation relating to the use and storage of human tissue for research purposes and such activities shall at least meet the requirements as set out in the 2004 Human Tissue Act and the 2006 Human Tissue (Scotland) Act.

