#### 7.17. Protocol deviations

Major deviations from this protocol include mishandling of EC biopsy sample or blood, late processing of sample or incorrect storage of samples. These will be documented in the patients CRF and these samples may be excluded from analysis.

Minor deviation from this protocol is any other deviation not listed above. This will be documented and use to describe any outliers to the data in the final analysis

### 8. Progression to part 2

Progression to part 2 will only take place after review of data and adverse events from part 1 has been completed. The focus of the review will be to assess the variability of the data collected from part 1. If the variability is as predicted or less, no changes to the protocol will be made. If the variability is greater than expected, then the power will be recalculated. Based on the updated sample size, we will then reassess requirement for the current predicted sampling for part 2.

Progression to part 2 will happen after an amendment to the protocol has been made confirming sample size requirement and sampling requirements.

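### Section 7.13 withdraws participants from the study rather than from further biopsies, so samples already taken can lose later AE data and the 28-day outcome.

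*Protocol*

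**What the plan says.** Section 7.13 has two routes out of the study, and both end participation as a whole.

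- **SAE route, mandatory.** The trial team will "withdraw patients from the study if the patient has suffered an serious adverse event (SAE) as a consequence of the trial procedures".
- **Physician route, discretionary.** The treating physician may withdraw the patient from the study "if they believe that it is causing them significant harm or inappropriate to perform the procedure".

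For both routes, "In both cases it must be explicitly documented in the eCRF the reason/s for withdrawal". On replacement: "Participants who are prematurely withdrawn may be replaced at the decision of the study team". No criteria or limit are given.

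The follow-up text does not mention withdrawn participants. Section 7.12 says "Follow up will take place at 28 days (±2 days) post enrolment", takes the status from the clinical notes, and adds "No formal contact will be made with the patient, unless there are any outstanding AEs that require resolving". Section 9.1 collects AEs from consent to the end of follow-up. Section 7.10, writing about participants who withdraw themselves, says that data and samples up to the "point of withdrawal will be used after withdrawal unless the participant has explicitly said so". It provides for nothing after that point.

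**The concern.** A procedure-related SAE, or a judgement that a biopsy is inappropriate, is a reason to stop sampling. It is not in itself a reason to stop observing, yet the protocol has no status for a participant who stops biopsies and stays in the study.

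The Aims in section 5 relate endothelial expression to clinical features and to patient outcome, and section 6.1 schedules a 28-day survival outcome in every patient cohort. A participant withdrawn after a biopsy leaves an expression sample with no provision for that outcome.

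The loss may also be selective. In the Part 2 sepsis cohort, biopsies are planned on admission and at 24 and 48 hours. Patients judged unsuitable for a repeat biopsy are plausibly the sicker ones. If they leave without an outcome and are replaced, the patients with linked expression and outcome would be less severely ill than those enrolled.

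An analysis plan cannot repair this later, because a status that was never recorded cannot be analysed.

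**Working it through.** **1. What is kept and what is not, for a participant withdrawn under 7.13**

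| Item | Provision | Kept? |
|---|---|---|
| Triggering SAE | Reason in eCRF (7.13); SAE reported within 24 hours (9.1); study ends only when AEs are resolved (7.14) | Yes |
| Samples and data up to withdrawal | Used by default (7.10, written for self-withdrawal) | Yes, on a reasonable reading |
| New AEs after withdrawal | 9.1 runs to the end of follow-up; withdrawn participants not mentioned | Not provided for |
| 28-day status | 7.12 reads the notes; withdrawn participants not mentioned | Not provided for |

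The gap is in the last two rows.

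**2. Is replacement needed to protect power?**

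Section 10.2 gives a difference of 2, variability 2 (read as the SD), alpha 0.05 (taken as two-sided) and power 0.8, with about 17 patients (read as per group). The standardised difference is 2/2 = 1. The normal approximation gives 16 per group. The exact t calculation gives 16.7, so 17, and the stated figure is reproduced.

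Exact-t power by number per group:

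- 20: 0.869
- 18: 0.830
- 17: 0.807
- 16: 0.781

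On these inputs, Part 2 can lose 20 − 17 = 3 per cohort and keep 80% power. Part 1 recruits 20 against a stated 16 (not re-run here), a margin of 4, but section 10.1 sets that margin aside for unusable mRNA. No sample-size figure changes under this point.

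**3. How often might the SAE route be used?**

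The pilot reported no related serious AEs, with peripheral biopsy in 16 patients (sections 5 and 7.15). The exact one-sided 95% upper limit for 0 of 16 is 1 − 0.05^(1/16) = 17.1%. Such withdrawals are probably few but are not excluded.

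**4. Illustration of selection (assumed figures, not from the protocol)**

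Let p be the true 28-day mortality, q = 60% the mortality among those withdrawn, and k of 20 the number withdrawn and replaced by patients like those retained. Mortality in the resulting cohort is r = (p − q·k/20)/(1 − k/20).

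| p | k = 1 | k = 2 | k = 4 |
|---|---|---|---|
| 20% | 17.9% | 15.6% | 10.0% |
| 30% | 28.4% | 26.7% | 22.5% |
| 40% | 38.9% | 37.8% | 35.0% |

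For example, p = 30% and k = 2 gives (0.30 − 0.06)/0.90 = 26.7%. This shows the direction of a shift in case mix. It does not measure bias in the expression-outcome relation, which cannot be computed from the protocol.

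**The case against.** The strongest reply is that the protocol never says record review stops at withdrawal. Sections 7.12 and 9.1 make no exception for withdrawn participants, so a team could go on reading the notes. That is possible, but withdrawal from the study ordinarily ends study data collection, and 7.10 speaks only of data up to that point. The text should not leave this to interpretation.

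Four further points stand, and they limit the claim.

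- **Safety data.** A reader might infer that safety data on the triggering event are lost, or that the review before Part 2 is weakened. The text does not support this. That review needs "review of data and adverse events from part 1 has been completed" (section 8), and the triggering SAE is documented, reported and followed to resolution. Part 1 participants have one biopsy, so a biopsy-related SAE comes after it and is available to the review.
- **Discretion.** A reader might infer that anyone judged unsuitable for biopsy must leave and be replaced. The physician route and replacement are only permitted. Section 7.15 sets three biopsies as a Part 2 maximum, so missing one does not force a swap. Section 8 also requires an amendment confirming Part 2 sampling.
- **Part 1.** A patient withdrawn before the single biopsy has no expression sample to relate to outcome. Selection is therefore a weaker concern in Part 1.
- **Size.** The illustration is wholly assumed, and its shifts are small against sampling error. At 30% mortality in 20 patients the standard error is √(0.3 × 0.7/20) = 10.2 percentage points, against a shift of 3.3 points for k = 2. The study's target is also not mortality itself.

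**Conclusion.** The point holds in a limited form. Section 7.13 ends study participation where ending study procedures would be enough, and no section keeps those participants in later AE collection or the 28-day check. Samples already taken can therefore lose their linked outcome, at 5% of a patient cohort for each withdrawal.

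Bias in the expression-outcome relation is conditional. It needs withdrawal to depend on illness severity, which is most plausible for serial biopsies in the Part 2 sepsis cohort, and the protocol gives no figure for its size. That replacement would select fitter patients is a plausible inference, not something the text establishes.

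This is an inexpensive improvement to a conduct rule. It is not a flaw in the sample size or in the safety review.

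**What to change.** In section 7.13, define two separate states:

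- **No further study procedures.** This covers the SAE route and the physician route. The participant stays enrolled for AE collection and for the 28-day status from clinical notes under 7.12. Existing samples and data stay in the analysis even if a replacement is recruited.
- **Withdrawal of consent.** This is the participant's own decision and is handled under 7.10.

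Who stops biopsies, and when, remains the clinicians' decision and is not touched.

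The cost is a wording change and a few extra note reviews at day 28, without patient contact unless an AE is outstanding. One consequential edit follows: the identifier ranges in 13.4 stop at 20 per patient cohort per part, so a replacement recruited alongside a retained participant would need a further code. The amendment that section 8 already requires before Part 2 could carry the change, although an earlier amendment would also cover Part 1.
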